### 10.8.3 Amended protocol [03] (29 April 2020)

This amended protocol 03 (amendment 03) is considered to be nonsubstantial based on the criteria set forth in Article 10(a) of Directive 2001/20/EC of the European Parliament and the Council of the European Union.

### OVERALL RATIONALE FOR THE AMENDMENT

To clarify language regarding interim analysis.

**Protocol amendment summary of changes table**

Section # and Name	Description of Change	Brief Rationale
Section 1.1 Synopsis and Section 10.2: Clinical Laboratory Tests	Remove requirement that the interim analysis requires data up to Day 15.	Clarifies the scope of adaptations the Sponsor may make based on the interim analysis results
1.3 Schedule of Activities (SoA)	Clarified PK sample collection for Day 2 and Day 3. Removed 'optional' for the serum sIL-6R.	Provided clarity on PK and serum sIL-6R collection
Section 2.3 Benefit/Risk Assessment	Changed multisystem organ dysfunction to multi-organ dysfunction	Corrected to align with the publication where it is described (16)
Section 4.1 Overall design	Clarified that IDMC will actively monitor interim data, and also make recommendations pertaining to the eligible population throughout the course of the study.	Clarification
Section 5.2 Exclusion criteria	Removes the use of vasopressors as a factor to be considered for selection criterion E01.	Vasopressors are also used by critical patients and not primarily patients with multi organ disease (who are excluded).
And Section 9.5 Interim analysis	Specify the type of modifications that the Sponsor may make based on the interim analysis results.	Clarifies the scope of adaptations the Sponsor may make based on the interim analysis results

SAP	Statistical analysis plan
SARS-CoV-2	Severe acute respiratory syndrome coronavirus 2
SAS	Statistical Analysis System
SC	Subcutaneous
SOC	System organ class
sIL-6R	Soluble interleukin-6 receptor
SpO ₂	Peripheral capillary oxygen saturation
SUSAR	Suspected unexpected serious adverse reaction
TEAE	Treatment-emergent adverse event
WBC	White blood cell
WHO	World Health Organization

1 OVERVIEW AND INVESTIGATIONAL PLAN

1.1 STUDY DESIGN AND RANDOMIZATION

This study is a randomized, double-blind, placebo-controlled, phase 3 trial to evaluate the efficacy and safety of sarilumab in hospitalized adults with severe or critical COVID-19. The study will be conducted in Europe and other countries except in the United States (US) in up to 100 sites.

Approximately 400 patients will be randomized via interactive response technology (IRT) in a 2:2:1 allocation ratio to sarilumab 400 mg IV, sarilumab 200 mg IV, or placebo. Randomization will be stratified by severity of illness (severe, critical) and use of systemic corticosteroids (yes, no), and balanced by region. All patients will receive a single dose of study drug on Day 1. Patients may receive a second dose with study drug (based on the original treatment group assigned) 24 to 48 hours after the first dose, if they meet prespecified criteria in protocol.

Severity of illness categories:

- Severe disease:
 - Requires supplemental oxygen administration by nasal cannula, simple face mask, or other similar oxygen delivery device
- Critical disease:
 - Requires supplemental oxygen requiring delivered by non-rebreather mask or high flow nasal cannula, or
 - Use of invasive or non-invasive ventilation, or
 - Requiring treatment in an intensive care unit.

Patients will be assessed daily while hospitalized. Patients discharged from the hospital prior to Day 29 will be contacted with a follow-up phone call on Day 29 to assess status and occurrence of re-admission to a hospital. Patients will undergo a series of efficacy, safety and laboratory assessments while in the hospital. Serum IL-6 and other markers will be collected and analyzed in a central laboratory. Nasopharyngeal (NP) samples to monitor viral infection and blood samples may be obtained on Day 1 (pre-dose), 4, 7, 15, 29 (or up until the day of discharge if the patient is discharged from the hospital before Day 29). An individual patient will complete the study approximately 60 days from screening to follow-up on day 60 ± 7 days. Patients will not be required to return to the hospital once discharged.

1.2 OBJECTIVES

1.2.1 Primary objective

To evaluate the clinical efficacy of sarilumab relative to the control arm in adult patients hospitalized with severe or critical COVID-19.

1.2.2 Secondary objectives

- Evaluate the 28-day survival rate
- Evaluate the clinical efficacy of sarilumab compared to the control arm by clinical severity
- Evaluate changes in the National Early Warning Score 2 (NEWS2)
- Evaluate the duration of predefined symptoms and signs (if applicable)
- Evaluate the duration of supplemental oxygen dependency (if applicable)
- Evaluate the incidence of new mechanical ventilation use during the study
- Evaluate the duration of new mechanical ventilation use during the Study
- Evaluate the proportion of patients requiring rescue medication during the 28-day period
- Evaluate need for admission into intensive care unit (ICU)
- Evaluate duration of hospitalization (days)
- The secondary safety objectives of the study are to evaluate the safety of sarilumab through hospitalization (up to Day 29 if patient is still hospitalized) compared to the control arm as assessed by incidence of:
 - Serious adverse events (SAEs)
 - Major or opportunistic bacterial or fungal infections in patients with grade 4 neutropenia
 - Grade ≥ 2 infusion related reactions
 - Grade ≥ 2 hypersensitivity reactions
 - Increase in alanine transaminase (ALT) $\geq 3X$ ULN (for patients with normal baseline) or $>3X$ ULN and at least 2-fold increase from baseline value (for patients with abnormal baseline)
 - Major or opportunistic bacterial or fungal infections

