### 3 OBJECTIVES AND ENDPOINTS

**Table 1 - Objectives**

Primary Objectives

• To evaluate the clinical efficacy of sarilumab relative to the control arm in adult patients hospitalized with severe or critical COVID-19

Secondary Objectives

• Evaluate the 28-day survival rate

• Evaluate the clinical efficacy of sarilumab compared to the control arm by clinical severity

• Evaluate changes in the National Early Warning Score 2 (NEWS2)

• Evaluate the duration of predefined symptoms and signs (if applicable)

• Evaluate the duration of supplemental oxygen dependency (if applicable)

• Evaluate the incidence of new mechanical ventilation use during the study

• Evaluate the duration of new mechanical ventilation use during the Study

• Evaluate the proportion of patients requiring rescue medication during the 28-day period

• Evaluate need for admission into intensive care unit (ICU)

• Evaluate duration of hospitalization (days)

• The secondary safety objectives of the study are to evaluate the safety of sarilumab through hospitalization (up to day 29 if patient is still hospitalized) compared to the control arm as assessed by incidence of:

- Serious adverse events (SAEs)

- major or opportunistic bacterial or fungal infections in patients with grade 4 neutropenia

- Grade <math>\geq 2</math> infusion related reactions

- Grade <math>\geq 2</math> hypersensitivity reactions

- Increase in alanine transaminase (ALT) <math>\geq 3X</math> ULN (for patients with normal baseline) or <math>>3X</math> ULN AND at least 2-fold increase from baseline value (for patients with abnormal baseline)

- major or opportunistic bacterial or fungal infections

Tertiary/exploratory

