### **9.4.3.2 Safety**

#### **9.4.3.2.1 Adverse events**

Definitions

For safety variables, the following observation period is defined:

The on-treatment period is defined as the day from first dose of study drug to the last dose of study drug plus 60 days.

Treatment-emergent adverse events (TEAEs) are defined as those that are not present at baseline or represent the exacerbation of a pre-existing condition during the on-treatment period.

In addition, there will be an end of study (EOS) phone call follow-up to determine the vital status (alive or dead) of the patient and to assess for SAEs and AESI.

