2.1.4 Safety endpoints

The safety analysis will be based on the reported adverse events (AEs), serious AEs (SAEs) and adverse events of special interest (AESIs). Other safety information, such as clinical laboratory data, and vital signs will also be assessed as applicable.

Observation period

There are 3 parts in the observation period:

- **Screening** period is defined as the time from the signed informed consent date up to the time prior to first dose of IMP.
- **On-treatment** period is defined as the day from the first dose of the IMP to the last dose of the IMP + 60 days.
- **Post-treatment** period is defined as the time after the last dose of IMP +60 days.

The treatment-emergent adverse event (TEAE) period is the **on-treatment** period.

The on-study observation period is defined as the time from start of treatment until the end of the study (defined as last protocol planned visit or the resolution/stabilization of all serious adverse events and AESI).

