2.4.5.1 Analyses of adverse events

Generalities

The primary focus of adverse event reporting will be on treatment-emergent adverse events. Pretreatment and posttreatment adverse events will be described separately.

If an adverse event date/time of onset (occurrence, worsening, or becoming serious) is incomplete, an imputation algorithm will be used to classify the adverse event as pretreatment, treatment-emergent, or posttreatment. The algorithm for imputing date/time of onset will be conservative and will classify an adverse event as treatment emergent unless there is definitive information to determine it is pretreatment or posttreatment. Details on classification of adverse events with missing or partial onset dates are provided in [Section 2.5.3](#).

Adverse event incidence tables will be sorted by SOC internationally agreed order and HLGT, HLT, PT by alphabetic order. For adverse event incidence tables presented by SOC and PT, they will be sorted by the internationally agreed SOC order and by decreasing incidence of PTs based

on the Sarilumab 400 mg IV group within each SOC, for the number (n) and percentage (%) of patients experiencing an adverse event. Multiple occurrences of the same event in the same patient will be counted only once in the tables within a treatment phase. The denominator for computation of percentages is the safety population within each treatment group.

Analysis of all treatment-emergent adverse events

The following treatment-emergent adverse event summaries will be generated for the safety population.

- Overview of treatment-emergent adverse events, summarizing total number or number (%) of patients with any
 - Treatment-emergent adverse event
 - Serious treatment-emergent adverse event
 - Severe treatment-emergent adverse event
 - AESI
 - Treatment-emergent adverse event leading to death
 - TEAE leading to study drug interruption or discontinuation
- All treatment-emergent adverse event by primary SOC, HLT, and PT, showing the number (%) of patients with at least 1 treatment-emergent adverse event.
- All treatment-emergent adverse events by primary SOC and PT, showing the number (%) of patients with at least 1 treatment-emergent adverse event.
- All treatment-emergent adverse events by primary SOC, PT and CTC grade, showing the number (%) of patients with at least 1 treatment-emergent adverse event.

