- All treatment-emergent adverse events regardless of relationship and related by primary SOC and PT, showing the number (%) of patients with at least 1 treatment-emergent adverse event.
- All treatment-emergent adverse events leading to study drug interruption or discontinuation by Primary SOC and PT, showing the number (%) of patients with at least 1 treatment-emergent adverse event.

Analysis of all treatment emergent serious adverse event(s)

- All treatment-emergent serious adverse events by primary SOC and PT showing the number (%) of patients with at least 1 serious treatment-emergent adverse event.
- All treatment-emergent serious adverse events regardless of relationship and related to IMP, by primary SOC, and PT, showing the number (%) of patients with at least 1 treatment-emergent serious adverse event.

Analysis adverse event of special interest

Unless otherwise specified, AESI will be summarized during the TEAE period by prespecified-grouping (AE category of interest), showing the number (%) of participants, sorted by decreasing

frequency of PT. In addition, summary of TEAE of infusion reactions, ALT increase, and infection events will be provided.

Listings of all adverse events, serious adverse events and AESIs during the study will be provided.

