4 DATABASE LOCK

The primary analysis is planned when the last patient randomized reaches Day 29 (or planned Day 29 if the patient is discharged or leaves the study early). Final analysis will be performed at study end (ie, Day 60).

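### The safety objective runs through hospitalization to Day 29, but SAEs and AESIs are counted to last dose + 60 days as crude percentages, a window that an estimated third of patients have not completed at the primary lock

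*SAP*

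**What the plan says.** **Objective.** SAP 1.2.2 sets out to "evaluate the safety of sarilumab through hospitalization (up to Day 29 if patient is still hospitalized) compared to the control arm", with SAEs first on its list. Protocol Table 1 has the same limit: "evaluate the safety of sarilumab through hospitalization (up to day 29 if patient is still hospitalized".

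**Counting window.** In SAP 2.1.4 the on-treatment "period is defined as the day from the first dose of the IMP to the last dose of the IMP + 60 days", and the treatment-emergent period is set equal to it. The definition is also in Protocol 9.4.3.2.1: "The on-treatment period is defined as the day from first dose of study drug to the last dose of study drug plus 60 days". The mismatch is therefore in both documents.

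**Tables.** SAP 2.4.5.1 plans "All treatment-emergent serious adverse events by primary SOC and PT showing the number (%) of patients", and states that "AESI will be summarized during the TEAE period by prespecified-grouping (AE category of interest". On percentages: "The denominator for computation of percentages is the safety population within each treatment group". It plans no summary cut at discharge or Day 29, and no person-time or Kaplan-Meier incidence for adverse events. The SAE endpoint in Protocol Table 2 carries no time limit.

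**Timing.** SAP section 4: "The primary analysis is planned when the last patient randomized reaches Day 29". A final analysis follows at study end, Day 60. Neither document says which of the two supplies the safety tables.

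**The concern.** Two things do not line up. First, the objective asks about one period and every adverse event table reports another, so the stated safety question has no planned analysis.

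Second, at the primary lock the longer window is still open for patients enrolled late. A crude percentage counts such a patient in full in the denominator although part of the window has not yet been observed. The reported incidence then depends on the calendar date of the lock. It also depends on when each arm enrolled, which matters because Amended Protocol 04 closed the 200 mg arm while 400 mg and placebo continued at 2:1. SAP version 2 (5 May 2020) predates that amendment (11 June 2020) and has no rule for it. At stake is how far SAE and infection percentages at the primary analysis can be read across arms.

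**Working it through.** The plan gives no figure for safety follow-up at the lock, so there is none to reproduce.

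**Inputs from the documents**
- Accrual A of about 90 days, each patient followed at least 29 days (Protocol 9.2, SAP 1.3).
- Lock when the last randomized patient reaches Day 29 (SAP 4).
- Last day of the window, D: with first dose on Day 1, last dose + 60 days is Day 61 after one dose and Day 62–63 after a second dose 24–48 hours later. The study ends nominally at Day 60.
- Amendment 02 (8 April 2020) describes enrollment as already rapid. Amendment 04, closing 200 mg, is dated 11 June 2020, 64 days later.

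**Assumed, not in the documents**
- Uniform accrual.
- An SAE hazard identical in all arms: 0.6% per day to Day 29, then h = 0.1, 0.2 or 0.3% per day.

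**1. Share short of the window at the lock** = (D − 29)/A.
- Day 60: 31/90 = 34.4%. Day 61: 32/90 = 35.6%, about 142 of 400. Day 63: 34/90 = 37.8%.
- Day 61 with 150-day accrual: 32/150 = 21%. With 60-day accrual: 32/60 = 53%. The amendment dates imply at least 64 days of accrual (32/64 = 50%), so 53% is just beyond the extreme.
- Mean shortfall to Day 61: (32²/2)/90 = 5.7 of 60 days per patient.

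**2. 400 mg versus placebo.** Allocation is 2:1 before and after Amendment 04, so both arms have the same enrollment-date distribution in expectation. Truncation lowers both incidences and favours neither.

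**3. 200 mg versus placebo.** Within a 90-day accrual the dates put closure at day 64 or later. Patients enrolled after day 90 − 31 = 59 are short of Day 60.
- 200 mg, closure on day 64: (64 − 59)/64 = 7.8%.
- Placebo, total enrollment rate constant (share 1/5 before closure, 1/3 after): (5/5 + 26/3)/(64/5 + 26/3) = 9.67/21.47 = 45%. If placebo enrollment is spread evenly: 34%.

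**4. Gap with no true effect.** For follow-up t, I(t) = 1 − exp{−[0.006 × 29 + h × (min(t, 60) − 29)]}. This gives I(29) = 16.0% and I(60) = 18.5, 21.0 and 23.4% for the three values of h. Averaging I(t) over each arm's follow-up at the lock:

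| Scenario | 200 mg (%) | Placebo (%) | Gap (points) |
|---|---|---|---|
| Closure day 64, constant total rate | 18.5, 21.0, 23.4 | 17.9, 19.8, 21.7 | 0.6, 1.2, 1.7 |
| Closure day 85, placebo spread evenly | 18.2, 20.4, 22.5 | 18.1, 20.2, 22.2 | 0.1, 0.2, 0.3 |

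The range is roughly 0.1–1.7 points. With a common Day 29 window every arm has I(29) = 16.0% and the gap is zero.

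This treats observation as continuous. Discharged patients have scheduled adverse event contacts only at Day 29 and end of study (Schedule of Activities, footnotes 3 and 4). In the extreme where no truncated patient contributes anything after Day 29, the first scenario gives (45.0% − 7.8%) × (I(60) − 16.0%), about 1.0–2.8 points. Inpatients are assessed daily, so this is an upper limit for that scenario.

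**5. Scale.** Standard error of the difference at 20% incidence: √[0.16 × (1/160 + 1/80)] = 5.5 points at the planned sizes. If closure falls halfway through 400 patients, 200 mg has 200 × 2/5 = 80 and placebo 200/5 + 200/3 = 107, giving √[0.16 × (1/80 + 1/107)] = 5.9 points.

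**The case against.** The strongest reply is that this is a wording mismatch with little consequence.

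- **A Day 60 final analysis is planned.** Follow-up then essentially fills the window, apart from 1–3 days and the ±7-day visit allowance. Its supportive status is stated under multiplicity, not as a rule about safety tables. This stands. It largely removes the truncation, but those tables still do not match the Day 29 objective.
- **Several AESIs barely depend on days 30–60.** Infusion reactions are limited to 24 hours, overdose is tied to dosing, and neutropenia and ALT rise rely on laboratory values scheduled only to Day 29 or discharge. This stands, and narrows the point to SAEs and infections. Day 29 survival already has its own analysis as the key secondary endpoint.
- **The gap is small and nothing is tested.** Adverse event summaries are descriptive. This also stands, and it limits the weight of the point.
- **Aligning the objective to Day 60 would be equally valid.** It would cure the wording, but leave the primary-lock percentages with unequal follow-up.

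A reader might go further and infer that the main 400 mg comparison is biased. Concurrent 2:1 randomization throughout does not support that. A reader might also infer that every 200 mg patient has the full window at the lock while a third of placebo does not. Under 90-day accrual the amendment dates make that unlikely: closure falls no earlier than about day 64, leaving about 8% or more of 200 mg truncated.

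**Conclusion.** The mismatch is textual and certain: no planned adverse event table answers the safety objective as written. The incomplete window at the primary lock is an inference. It affects 34–36% of patients under uniform 90-day accrual and moves with the length and shape of accrual.

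The consequence is modest. Incidence at that lock mixes follow-up lengths, and 200 mg versus placebo is compared over unequal observation time, with a null gap of roughly 0.1–1.7 points on hazards the documents do not supply. That is small against a standard error of 5.5–6 points. Nothing here shows that a safety conclusion would be reversed, or that the last dose + 60 days tables should be withheld from the primary analysis. The point is worth correcting because the correction is cheap.

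**What to change.** 1. At the primary analysis, add SAE and infection/AESI incidence tables over one fixed window, first dose to Day 29, for every patient whether discharged or not. Use these for between-arm comparison. Cutting at discharge instead would make observation time depend on recovery.
2. Word the objective in Protocol Table 1 and SAP 1.2.2 to the same window.
3. Keep the last dose + 60 days tables. Treat the Day 60 final analysis as their complete version, and label any shown at the primary lock as having incomplete follow-up.

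No new data are needed, since the Day 29 call already collects all adverse events from discharged patients. The cost is a wording change in both documents and one extra set of tables with a date cut.

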1.3 DETERMINATION OF SAMPLE SIZE

[figure not shown]
The sample size calculations are performed based on the primary endpoint, the time to improvement of 2 points in clinical status assessment from baseline using the 7-point ordinal scale.

Assuming that accrual duration is 3 months (~90 days) with each patient followed for a period of at least 29 days, the proportions of patients with two points improvement from baseline in clinical status assessment at Day 15 are 45% and 70% for placebo and sarilumab, respectively, a total sample size of approximately 400 patients with a 2:2:1 randomization ratio provides at least 90% power for pairwise comparisons between each sarilumab dose (400 mg IV or 200 mg IV; n~160 each) and placebo (n~80), using a log-rank test of superiority at a two-sided significance level of 0.05. Sample size calculation was performed using PASS 14.

1.4 STUDY PLAN

The schedule of activities can be found in Section 1.3 of the study protocol. The graphical study design is provided in [Figure 1](#).

Figure 1 - Graphical study design

* If the patients has been discharged from the hospital before Day 29, the study site staff will contact the patient for a follow-up phone call
 ** The EOS will be on Day 60 or day of death, whichever comes first. If the patient has been discharged from the hospital before Day 60, the study site staff will contact the patient for a follow-up phone call

R: Randomized; EOS: End of study; IV: intravenous; N: number

1.5 MODIFICATIONS TO THE STATISTICAL SECTION OF THE PROTOCOL

The original protocol (dated: 18 March 2020) was updated to amendment 01 (dated: 26 March 2020), and amendment 02 (dated: 8 April 2020). The [Table 1](#) below gives the timing, rationale, and key details of major changes to the protocol statistical section.

Table 1 – Protocol amendment statistical changes

Amendment Number	Date Approved	Rational	Description of statistical changes
01	26-Mar-2020	To provide power calculation for both phase 2 and phase 3 primary endpoints	
 The power calculation for phase 3 primary endpoint was added

		To specify the multiplicity control method	
 • Details of the multiplicity control method were added
		To specify interim analysis	
 • A planed analysis at the end of Phase 2 was added in Interim Analysis section
02	08-Apr-2020	Study design was changed from adaptive phase 2/3 to adaptive phase 3, and new primary and key secondary endpoints were specified	
 • Updated the sample size/power calculation based on the new primary endpoint, • Change total number of patients needed from 300 to 400 in sample size section • Updated the analyses of the primary and key secondary endpoints • Multiplicity control method was revised • Interim analysis at ~50% of total planned number of patients (~200) was added to replace the end of phase 2 analysis
03	29-Apr-2020	To clarify the scope of adaptations the Sponsor may make based on the interim analysis results	
 • Remove requirement that the interim analysis requires data up to Day 15 • Specify the type of modifications that the Sponsor may make based on the interim analysis results

